Study population: Patients hospitalized for cellulitis, > 18 years of age.

Power calculation (non-inferiority design): a total sample size of 316 randomized patients gives 80% power to reject the null hypothesis of non-inferiority assuming a 15% failure rate, considering a difference of 10% as equivalence limit, with a 0.05 significance level.

Intervention: 6 days of flucloxacillin followed by another 6 days of flucloxacillin or placebo.

Main study parameters/endpoints: The primary endpoint is resolution of cellulitis at 14 days, defined as disappearance of warmth and tenderness at the site of infection, with substantial improvement in erythema and edema, and without recurrence by day 28, defined as the need of additional antibiotic therapy for cellulitis.

Secondary study endpoints include a test of cure with a different set of criteria for cure by day 14 and relapse by day 28, recurrence of cellulitis by day 90, speed of recovery as determined by improvement in cellulitis severity score and self assessment of subjective pain and swelling on VAS scales (0-10), Health-related Quality of Life (Dutch SF-36 questionnaire), and health care resource utilisation as determined by total antibiotic use and effect on direct and indirect health-care associated costs (economic evaluation and budget impact analysis).

Statistical analysis: Analysis will be based on intention-to-treat basis. Groups will be compared for the primary endpoint with Chi-squared test and Cochran-Mantel-Haenszel test for adjustment for the baseline covariates to evaluate the non-inferiority hypothesis. Secondary outcome parameters will be analyzed using Chi-squared test, two group t-test or Mann-Whitney test when appropriate.

Nature and extent of the burden and risks associated with participation: All study participants will have to complete a maximum of five sets of questionnaires (some by phone) and a maximum of five venous punctures. Potential risks include inferiority of 6 days of antibiotics compared to 12 days of treatment, i.e. a slower recovery of patients in the intervention group. Given the results of earlier trials on shortening of antibiotic therapy in pneumonia and urinary tract infections, we do not expect this to be the case. In our view the

small risk that 6 days will be inferior compared to 12 days offsets the profits which a shortening of antibiotic therapy for cellulitis potentially yields.

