3.3 Time schedule of study procedures for participants

	Day 0	Day 2-3	Day 5-6	Day 14-15	Day 28-29	Day 90
Informed consent	X					
In- and exclusion criteria	X					
Physical examination	X		X	X	X	
Laboratory measurements (usual care)	X					
Venous puncture	X	X	X	X	X	
Skin biopsy (see chapter 7)	X					
Clinical cellulitis score	X	X	X	X	X	
Self assessment score (0-10 scale)	X	X	X	X	X	X
SF-36 questionnaire & EQ-5D	X				X	X
Health care utilization questionnaire			X		X	X
Skin swabs (see chapter 7)	X			X		

Table 1. Time table of study procedures for participants

Up to day 28-29, patients will be evaluated face to face either in the clinic or at home. Self assessment scores and questionnaires to be performed on day 90 will be mailed to patients beforehand. On day 90, the investigators will review the answers and scores by telephone. Laboratory measurements collected through usual care will be collected when available. In exceptional cases, where inclusion would be hampered by people's willingness or ability to have so many follow-up visits, the decision can be made by the investigators to perform the day 28-29 visit solely by telephone. In this case the primary endpoint, questionnaires and medication information would be assessable. Physical examination, cellulitis severity score measurement and blood collection will not be possible.

The above table displays the ideal time schedule for participants. However, patients can be included until 72 hours after admission. When patients are included during 24-72 hours, the day 2-3 visit is skipped. The check for improvement on day 5-6 then also allows for self-reported improvement as marker for clinical improvement, due to the investigator not being present at the time when the disease was likely at its most severe. Self-reported improvement is also rated using the seven aspects of the cellulitis severity score; patients will be asked if they think that they have improved, taking all those aspects into account.

[figure not shown]

Figure 1. Flow diagram for study participants**3.4 Time schedule of the study**

Months 1-4:	Preparation of study and obtaining ethical approval
Months 5-44:	Enrolment of patients
Month 44:	Last patient enrolled
Month 47:	Last follow-up visit of last enrolled patient
Months 47-48:	Analysis of results

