7.1.2 Secondary study endpoints

- Resolution of cellulitis at 14-15 days, defined as the absence of fever and an improvement of the combined symptom score of warmth, tenderness, erythema and edema by 2 or more points since patient inclusion (or it has reached 0), and without recurrence by day 28-29, defined as a stable or further improved combined symptom score, absence of fever and no need of additional antibiotic therapy for cellulitis.
 - A per protocol analysis of this endpoint (see paragraph 9.1).
 - Sensitivity analyses with two modifications to the day 28 criteria:
 - Resolution of cellulitis at 14 days, defined as the absence of fever and an improvement of the combined symptom score of warmth, tenderness, erythema and edema by 2 or more points since patient inclusion (or it has reached 0), and with further improvement of the combined symptom score of 1 or more point(s) (or it has reached 0), absence of fever, and no need of additional antibiotic therapy for cellulitis by day 28
 - Resolution of cellulitis at 14 days, defined as the absence of fever and an improvement of the combined symptom score of warmth, tenderness, erythema and edema by 2 or more points since patient inclusion (or it has reached 0), and with further improvement of the combined symptom score of 2 or more point(s) (or it has reached 0), absence of fever, and no need of additional antibiotic therapy for cellulitis by day 28
- Recurrence of cellulitis by day 90 after inclusion, defined as the need of additional antibiotic therapy for cellulitis
- Speed of recovery, as determined by improvement in cellulitis severity score, and self assessment of subjective pain and swelling on Visual Analog Scales scales (0-10), assessed at baseline (day 0), days 2-3, 5-6, 14-15, 28-29 and 90 (day 90 self-assessment only)¹²
- Mean health-related Quality of Life (using the Dutch SF-36 questionnaire and the EQ-5D) at day 0, 28-29 and 90.

- Health care resource utilisation, as determined by total antibiotic use and effect on direct and indirect health-care associated costs

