7.3.3 Quality of life

The Dutch SF-36 questionnaire will be used to assess health-related Quality of Life. This will be performed at inclusion and after 28-29 and 90 days. The SF-36 is a validated questionnaire²⁵, allowing the study population to be compared with equivalent controls in the general Dutch population.

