9. STATISTICAL ANALYSIS

9.1 General considerations

For the modified intention to treat analysis, all randomized patients who received at least one dose of study medication will be included. Missing data will be handled with multiple imputation, due to its nature of giving standard errors and P values that incorporate missing-data uncertainty²².

For the per protocol analyses, only randomized patients whose compliance was clear, and who received at least four days of trial medication (in clinical successes), or one day of trial medication (in clinical failures) will be included.

For the per protocol analysis of our primary outcome, patients are considered clinically cured if there is resolution of cellulitis at 14 days defined as disappearance of warmth and tenderness at the site of infection, with substantial improvement in erythema and edema, and without recurrence by day 28, defined as the need of additional antibiotic therapy for cellulitis. Clinical failure is defined as the persistence or progression of signs and symptoms of the acute process after randomization, or the inability to complete the study owing to adverse events. The response is deemed indeterminate when the patient (i) received less than 80% of the study drug for reasons other than clinical failure, (ii) acquired a concomitant infection outside of the skin requiring antibiotic treatment, (iii) was lost to follow-up, or (iv) died unrelated to the primary diagnosis.

For the per protocol analysis of our first secondary outcome (paragraph 7.1.2), patients are considered clinically cured if there is resolution of cellulitis at 14 days, defined as the absence of fever and an improvement of the combined symptom score of warmth, tenderness, erythema and edema by 2 or more points since patient inclusion (or it has reached 0), and without recurrence by day 28, defined as a stable or further improved combined symptom score, absence of fever and no need of additional antibiotic therapy for cellulitis. The response is deemed indeterminate when the patient (i) received less than 80% of the study drug for reasons other than unblinding / requiring new antibiotics for cellulitis / being unable to continue due to adverse effects, (ii) acquired a concomitant infection outside of the skin requiring antibiotic treatment, (iii) was lost to follow-up, or (iv) died unrelated to the primary diagnosis. Those whose outcomes are not cured or indeterminate are considered clinical failures.

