9.4 Secondary study parameter(s)

Differences in secondary outcome parameters will be reported as relative risk or mean difference (with 95% confidence interval), and p-values for statistical significance estimated with the Chi-square test, t-test or Mann-Whitney test, where appropriate. A Kaplan-Meier analysis will be performed to compare the time to relapse (defined as requiring additional antibiotics for cellulitis) between the two groups.

Variable/outcome	Hypothesis	Outcome measure	Methods of analysis
1. Primary			
Resolution without relapse	Intervention not inferior to control	Percent cured on day 14 without relapse by day 28 [binary]	Absolute risk difference
2. Secondary			
Resolution without relapse (per definition of protocol version 9.4, see paragraph 7.1.2, including both sensitivity analysis and per protocol analysis)	Intervention not inferior to control	Percent cured on day 14 without relapse by day 28 [binary]	Absolute risk difference (Per protocol analysis: χ^2 → Relative Risk)
Relapse by day 90	No difference	Percent with relapse [binary]	χ^2 → Relative Risk
Time to relapse	No difference	Relapse after cure [time to event]	Kaplan-Meier survival analysis
Objective speed of recovery	No difference	Cellulitis severity score [continuous]	Student's T-test or Mann-Whitney U test
Subjective speed of recovery	No difference	Visual analogue scales of pain and swelling [continuous]	Student's T-test or Mann-Whitney U test
Quality of life	No difference	SF-36 questionnaire score at day 0 and 90 compared to population, day 14 and 28 compared to day 5-6 [continuous]	Student's T-test or Mann-Whitney U test
Antibiotic usage	No difference	Total costs of antibiotic use [continuous]	Student's T-test or Mann-Whitney U test
Health care utilization	No difference	Total treatment associated costs, Health Care Utilization Questionnaire [continuous]	Student's T-test or Mann-Whitney U test
3. Subgroup analyses			
Cellulitis severity score on a continuous scale	Severity score affects rate of cure		Regression analysis, with interaction term for severity score
Diabetes mellitus vs no diabetes mellitus	Diabetes affects rate of cure		Regression analysis, with interaction term for (no) diabetes
4. Sensitivity analyses	Intervention not inferior to	All outcomes	

	control		
Per protocol analysis			Chi ² → Relative Risk
Primary outcome adjusted for baseline covariates			Cochran-Mantel-Haenszel → Relative Risk

Table 3. Analysis methods per outcome measures or variables

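### The quality-of-life row of Table 3 uses SF-36 scores at day 5-6 and day 14, when SF-36 is not collected, and gives no analysis of EQ-5D, in conflict with section 7.1.2

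*Combined protocol and SAP*

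**What the plan says.** Section 2.2 makes differences in quality of life a secondary objective. Section 7.1.2 turns this into an endpoint: "Mean health-related Quality of Life (using the Dutch SF-36 questionnaire and the EQ-5D) at day 0, 28-29 and 90". Section 7.3.3 says of the SF-36: "This will be performed at inclusion and after 28-29 and 90 days". In Table 1 of section 3.3, the row labelled "SF-36 questionnaire & EQ-5D" is marked at day 0, day 28-29 and day 90 and is blank at days 2-3, 5-6 and 14-15.

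The text of section 9.4 sets a general rule for secondary outcomes: a relative risk or a mean difference with a 95% confidence interval, tested by chi-square, t-test or Mann-Whitney. Table 3 then gives each outcome its own row. The quality-of-life row has a hypothesis of no difference, a t-test or Mann-Whitney test, and this outcome measure: "SF-36 questionnaire score at day 0 and 90 compared to population, day 14 and 28 compared to day 5-6".

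EQ-5D is not in that row or anywhere else in section 9. Section 7.3.4 gives it a part in a cost utility analysis, which section 9 does not describe. The Summary names only the SF-36 for quality of life.

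**The concern.** The row asks for SF-36 scores at visits where the questionnaire is not given. An analyst who follows Table 3 cannot run either change comparison, has no usable comparison at day 28-29 although SF-36 is collected then, and does not analyse EQ-5D. An analyst who follows 7.1.2 compares two instruments at two post-randomisation visits. The plan does not say which section prevails.

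The row also describes contrasts with the general population and with an earlier visit, whereas objective 2.2 needs a contrast between the two arms. No section names the SF-36 scale or summary score. The instrument, visit and score for a stated secondary objective could therefore be settled after the results are known.

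**Working it through.** No sample size or error rate underlies this point, so the check is a comparison of sections.

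**Days.**

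| Source | Instruments | Days |
|---|---|---|
| 3.3, Table 1 | SF-36, EQ-5D | 0, 28-29, 90 |
| 7.1.2 | SF-36, EQ-5D | 0, 28-29, 90 |
| 7.3.3 | SF-36 | inclusion, 28-29, 90 |
| 9.4, Table 3 | SF-36 | 0, 5-6, 14, 28, 90 |

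The first three sources agree. Because 7.1.2 and 7.3.3 give the days in prose, the result does not depend on how Table 1 was read. Of the five days in the Table 3 row, three match the schedule (0, 28 and 90) and two do not (5-6 and 14).

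**Comparisons in the row.**

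- Day 14 against day 5-6: neither score exists.
- Day 28 against day 5-6: the day 28-29 score exists, but its reference does not.
- Day 0 against the population: possible, but it precedes randomisation and says nothing about the arms.
- Day 90 against the population: possible. It yields a between-arm comparison only if it is read as a norm-referenced score that is then tested between arms.

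So 2 of 2 change comparisons cannot be computed. The post-randomisation SF-36 visits are days 28-29 and 90. The row covers at most one of them; 7.1.2 with the mean-difference rule in 9.4 covers both.

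**Imputation.** Section 9.1 states: "Missing data will be handled with multiple imputation". This cannot supply the absent visits. None of the 316 patients is scheduled for SF-36 at day 5-6 or day 14, so there are no observed values at those visits from which to build an imputation model.

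**EQ-5D.** Section 7.1.2 names two instruments and Table 3 names one. EQ-5D is mentioned 0 times in section 9.

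**Size of a corrected row.** With one SF-36 score and one EQ-5D index at two visits, there are 2 × 2 = 4 between-arm comparisons. With k SF-36 scores there are 2k + 2, so each further score adds two. That is why the score needs to be named.

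**The case against.** The strongest reply is that the intended analysis is clear. The rule in 9.4 stands directly above Table 3 and covers all secondary outcomes. Read with 7.1.2, it gives mean differences on both instruments at days 28-29 and 90. On that reading the row is a slip, no data are lost, and an analyst would put it right unprompted. This stands in part: the defect is one row set against an otherwise workable specification. But the row is the only place in section 9 that names quality-of-life time points, and what it names cannot be carried out. An evident intention makes the correction easy; it does not make the row correct. It also leaves the SF-36 score unnamed.

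A second reply is that EQ-5D may not have been meant as a quality-of-life outcome, since the Summary and 7.3.3 rely on the SF-36 alone and 7.3.4 links EQ-5D to costs. That makes this the weaker part of the point. Still, 7.1.2 does place EQ-5D in the endpoint, and section 9 mentions it under neither role.

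The comparison with the population is not an error in itself. Section 7.3.3 foresees it, describing the SF-36 as "allowing the study population to be compared with equivalent controls in the general Dutch population". Nor is any fault shown in the planned t-test or Mann-Whitney test.

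**Conclusion.** The concern holds. As written, the Table 3 row conflicts with sections 3.3, 7.1.2 and 7.3.3: two of its five days have no SF-36, neither change comparison can be computed, and day 28-29 has no usable comparison. EQ-5D has no stated analysis. The conclusion rests on the documents' own schedule and needs no outside assumption. The count of at most one between-arm visit under the row takes the generous reading of the day 90 entry.

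The unnamed SF-36 score is a related but separate gap, and it would remain if only the days were corrected. The effect is limited to the quality-of-life objective. The row should be corrected before unblinding.

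**What to change.** Replace the quality-of-life row of Table 3:

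- **Outcome measure:** one named SF-36 scale or summary score, and the EQ-5D index, at day 28-29 and day 90.
- **Method:** between-arm mean difference with 95% confidence interval, from a linear regression adjusted for the day-0 score. The adjustment is for precision; an unadjusted mean difference would resolve the conflict equally well.
- **Population comparison at days 0 and 90:** keep as descriptive.
- **EQ-5D:** state whether it is a quality-of-life endpoint (7.1.2), an input to the cost utility analysis (7.3.4), or both, and align the Summary.

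One option lies outside this row and is for precision only: the severity-score and VAS comparisons made after study medication starts could be adjusted for the day 5-6 value, which is already collected. The planned unadjusted tests remain valid without it.

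The cost is the wording of one row, a sentence on EQ-5D and the choice of an SF-36 score. Both instruments are already scheduled at days 0, 28-29 and 90. A day 28-29 visit held by telephone loses nothing here, since section 3.3 says: "In this case the primary endpoint, questionnaires and medication information would be assessable".

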2.2 Secondary objectives

- To assess differences in the frequency of relapse by day 90
- To assess differences in (A) speed of improvement of symptoms and (B) quality of life
- To assess the effects of 6 days of antibiotics compared to 12 days on total antibiotic use and health care costs

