7.3.4 Health care associated costs

Patient information on antibiotic use and health care utilization for cellulitis related complaints (e.g. outpatient services, inpatient admissions, other health care provider services, use of antibiotics and other medication, assist devices or materials) will be collected at certain intervals. This will be collected through Health Care Utilization Questionnaires and patient records at days 5-6, 28-29 and 90. Parallel to this analysis, the EQ-5D-3L questionnaire will be utilized to index the health state of the patients and to accentuate the cost utility analysis.

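### Table 3 measures total antibiotic use only by its cost, so the antibiotic days saved net of re-treatment have no prespecified estimate

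*Combined protocol and SAP*

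**What the plan says.** Section 2.2 sets as one secondary objective the effect of the two durations on "total antibiotic use and health care costs", which names two quantities. Section 7.1.2 repeats both in one endpoint: "Health care resource utilisation, as determined by total antibiotic use and effect on direct and indirect health-care associated costs". Neither section gives a unit for antibiotic use.

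The measure is fixed only in Table 3 (section 9.4). The row for antibiotic usage has the hypothesis "No difference", the outcome measure "Total costs of antibiotic use [continuous" and the method "Student's T-test or Mann-Whitney U test". The next row covers total treatment-associated costs. Both resource rows are therefore in money, and no row is in days, doses or defined daily doses.

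The text of 9.4 adds that secondary differences will be given as a relative risk or a mean difference with a 95% confidence interval. For this row that would be a mean difference in cost.

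The raw information is largely planned. Section 7.3.4 collects "Patient information on antibiotic use and health care utilization for cellulitis related complaints" at days 5-6, 28-29 and 90. Section 5.4 asks for capsules left at day 14-15. Section 11.1 collects antibiotics received after discharge from patients, with a pharmacy check when in doubt.

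**The concern.** The objective concerns exposure and the prespecified measure is expenditure. The two can diverge. Section 5.1 lets the timing of the oral switch, the dose, the dosing frequency and the empirical agent differ between patients, so two patients with equal antibiotic days can have unequal costs. The total also includes the first six days, which both arms share and which randomisation cannot affect.

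The hypothesis has a separate problem. One arm receives six more days of active drug by design, so whether use differs is not in question. The open quantity is how much of the six-day saving remains after re-treatment.

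Section 10.4 bases the benefit of a shorter course on less exposure (side effects, resistance selection, effects on the gut microbiota) and names relapse needing a new course as the individual risk. Net antibiotic days put that benefit and that risk on one scale. Without a prespecified definition, the exposure measure and its time window could be chosen after the results are known.

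**Working it through.** **The plan's own figure.** The documents give no figure for antibiotic use. The arm size used below comes from section 4.4 (success 85%, margin 10 points, one-sided 0.05, power 80%) and reproduces:

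n = (1.645 + 0.842)² × 2 × 0.85 × 0.15 / 0.10² = 157.7, so 158 per arm and 316 in total.

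**Equal days, unequal cost.** Section 5.1 mentions oral dosing from 500 mg four times daily to 1000 mg six times daily. In 500 mg capsules that is 4 to 12 a day, so six oral days are 24 to 72 capsules. The day count is the same and the quantity differs threefold, before any price is applied.

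**Net days saved.** The design difference is 12 − 6 = 6 active days (section 3.1). Let d be the excess proportion re-treated in the short arm and L the mean length of a re-treatment course, taken as equal in both arms and with full adherence:

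net saving = 6 − d × L.

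The documents fix no L. I assume 6 to 14 days; section 1 quotes 10 to 14 days as the guideline duration. I take d as 0, 5 or 10 points, also an assumption.

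| d | L = 6 | L = 10 | L = 14 |
|---|---|---|---|
| 0 | 6.0 | 6.0 | 6.0 |
| 0.05 | 5.7 | 5.5 | 5.3 |
| 0.10 | 5.4 | 5.0 | 4.6 |

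At L = 14 it would take d = 6/14, about 43 points, to cancel the saving.

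**Precision in days.** The 95% CI half-width is 1.96 × SD × √(2/158), with √(2/158) = 0.1125. For assumed SDs of 2, 4, 6, 8 and 10 days it is 0.44, 0.88, 1.32, 1.76 and 2.21 days.

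**Test of no difference in days.** In the least favourable case (difference 4.6, SD 10), power at two-sided 0.05 is Φ(4.6/1.125 − 1.96) = Φ(2.13) = 98%. Rejection is close to certain throughout these ranges, so the test says little and the interval carries the information.

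**Illustration on the cost scale.** The documents give no prices and no distribution of intravenous days. Assume an intravenous day costs r times an oral day, with intravenous days among the first six drawn with mean 4 and SD 1.5 and limited to 0-6. After limiting, the mean is about 3.94 and the SD about 1.38. Mean cost in the 12-day arm is 12 + (r − 1) × 3.94 oral-day units, its SD is (r − 1) × 1.38, and the arms differ by 6 units.

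| r | Saving as share of 12-day arm's cost | Saving in SDs | Power, 158 per arm, two-sided 0.05 |
|---|---|---|---|
| 5 | 6/27.8 = 22% | 1.1 | about 100% |
| 10 | 6/47.5 = 13% | 0.5 | about 99% |
| 20 | 6/86.9 = 7% | 0.2 | about 53% |

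In days of active drug the same contrast is 6 of 12, or 50% before re-treatment. This model includes no re-treatment and no variation in dose.

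**The case against.** The strongest reply is that nothing prevents the trial from reporting days. Section 7.1.2 keeps total antibiotic use as an endpoint, section 9.2 promises descriptive summaries of outcome parameters, 9.4 promises a mean difference with a confidence interval, and the data are mostly collected. This stands against the reading, which a reader might infer, that the trial cannot or will not estimate days saved. It does not meet the narrower point: the only measure the plan defines is cost, so the promised interval would be in money.

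Second, re-treatment is already analysed. Relapse by day 90 is defined by need for additional antibiotics, and 9.4 plans a Kaplan-Meier analysis of time to relapse. This partly stands. Those analyses give how often and when re-treatment occurs, but not how long it lasts. At 10 points of excess re-treatment, the assumed range of course length alone moves the net saving from 5.4 to 4.6 days.

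Third, a reader might infer that the cost test would wrongly suggest no difference in use when exposure is halved. The documents do not support that as a general claim. It rests on assumed prices, and in the illustration the cost test detects the difference almost always at ratios of 5 and 10. Only at 20 does power fall to about 53%. That most cost variation arises from intravenous days before randomisation is likewise an assumption of the model.

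Fourth, reduced exposure is not ranked as the trial's main rationale. Section 1 lists outcome, antibiotic use and health care resources together.

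**Conclusion.** The point holds as a mismatch between a stated objective and its prespecified measure. Antibiotic use is named separately from cost in 2.2 and 7.1.2, yet Table 3 defines it only as cost and attaches a hypothesis that is false for use by design. Following the plan to the letter gives no estimate of antibiotic days saved net of re-treatment.

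That quantity is about 4.6 to 6.0 days under the assumed excess re-treatment and course lengths, and would be estimable to about ±0.4 to ±2.2 days under the assumed SDs. The conclusion does not depend on these figures or on any price: at every price ratio the planned result is a difference in cost.

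The gap is confined to one secondary outcome. It does not affect the primary analysis or the 316-patient sample size, and it does not mean that the data are missing or that the cost comparison would fail.

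**What to change.** In Table 3, define antibiotic usage as days of active antibiotic per patient from randomisation to day 28 and to day 90. Count active study drug actually taken plus any additional antibiotics for cellulitis, and count placebo as zero. Counting all study-drug days would erase the contrast, since both arms take six days of capsules. Any open-label day left between randomisation and the first capsule is common to both arms and can be counted or not, provided the rule is stated.

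Replace the hypothesis of no difference with estimation: the mean difference with 95% CI. A Mann-Whitney test does not correspond to a mean difference and should not stand in for it. Keep antibiotic cost as a separate row in the cost analysis.

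Fix the definition before unblinding and derive the values afterwards, because the placebo rule needs the allocation.

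The cost is one revised row and one added row. The small downside is data work. The protocol does not state that start and stop dates of re-treatment courses are recorded, so their duration must be taken from the questionnaires, patient records and pharmacy checks.

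### The p-value for costs may come from a Mann-Whitney test, which does not test the mean cost difference that Section 9.4 promises to report and can disagree with its direction

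*Combined protocol and SAP*

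**What the plan says.** Section 2.2 sets the cost objective: "To assess the effects of 6 days of antibiotics compared to 12 days on total antibiotic use and health care costs". The Summary adds an "economic evaluation and budget impact analysis", and Section 7.3.4 says the EQ-5D-3L will be used "to accentuate the cost utility analysis". No method is given for any of these economic analyses.

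The only cost inference that is specified is in Section 9.4. Its text has two parts. The first fixes the effect measure: "Differences in secondary outcome parameters will be reported as relative risk or mean difference (with 95% confidence interval"). The second fixes the source of the p-value: "p-values for statistical significance estimated with the Chi-square test, t-test or Mann-Whitney test, where appropriate". Table 3 then lists two cost rows, one for the total cost of antibiotics and one for "Total treatment associated costs, Health Care Utilization Questionnaire [continuous". Both carry the entry "Student's T-test or Mann-Whitney U test".

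Resource use is collected through "Health Care Utilization Questionnaires and patient records at days 5-6, 28-29 and 90".

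**The concern.** The cost objective and a budget impact analysis both depend on the mean, because total spend equals mean cost per patient times the number of patients. Mann-Whitney compares ranks. A patient readmitted at great expense moves to the top of the ranking, but how expensive the readmission was hardly matters.

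This trial has the structure in which ranks and means can part. Nearly every 6-day patient avoids six days of active drug, a small saving shared by almost all. A few patients in either arm are readmitted at high cost. Section 1 says costs are driven mainly by hospitalisation and quotes relapse of 12 to 20%. Section 8.2.2 expects a significant share of patients to be readmitted. Section 10.7 names a higher relapse rate in the 6-day arm as a main risk.

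Skewed data are often taken as the reason to prefer a rank test, and the plan does not say otherwise. The report could then show a mean difference with one sign and a significant p-value that reflects a shift the other way. A reader would not know which one answers the cost question.

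**Working it through.** **Sample size used.** Section 4.4 gives 158 per group. With 85% success in both arms, a margin of 10 points, one-sided 0.05 and 80% power:

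n = (1.645 + 0.842)² × 2 × 0.85 × 0.15 / 0.10² = 157.7, so 158 per group and 316 in total, as stated. This calculation concerns the primary endpoint; the documents give no power or standard deviation for costs.

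**Assumptions.** All cost inputs and readmission rates below are assumed, because the documents give none. Tests are two-sided at 5%. In every scenario the true mean cost is higher in the 6-day arm, so a significant result of 6 days cheaper is wrong for the mean.

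**Model A: post-randomisation costs only.** Routine cost is lognormal with median 60 euro and log SD 0.5. The 12-day arm pays 15 euro more for antibiotics. A readmission costs 5000 euro.

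True mean difference (6-day minus 12-day) = (difference in readmission rate) × 5000 − 15.
- Readmission 14% vs 10%: 0.04 × 5000 − 15 = +185 euro.
- Readmission 16% vs 10%: 0.06 × 5000 − 15 = +285 euro.

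| Scenario | Mann-Whitney: 6-day arm significantly cheaper |
|---|---|
| 14% vs 10%, inputs as above | 82% (never dearer) |
| 16% vs 10%, inputs as above | about 71% |
| 14% vs 10%, saving 10 euro | 42% |
| 14% vs 10%, saving 5 euro | about 9% |
| 14% vs 10%, log SD 1.0 | about 31% |
| 14% vs 10%, median routine cost 150 euro | 12% |
| 14% vs 10%, median routine cost 300 euro | 2% to 3% |
| 14% vs 10%, plus index admission, median 3000 euro, log SD 0.1 to 0.5 | under 1% |
| 16% vs 10%, plus index admission, log SD 0.5 | 0.5% (dearer in 14%) |

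In the first row, 67% of all trials had both a significant Mann-Whitney result for 6 days cheaper and a higher observed mean in the 6-day arm. Welch's test gave the false result in well under 1% of trials in the first two rows.

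**Model B: index admission included throughout.** Index cost is lognormal with mean 4000 units, less a fixed saving in the 6-day arm, plus a skewed readmission cost with mean 8000.

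True mean difference = (difference in readmission rate) × 8000 − saving.

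| Saving | Log SD | Readmission | True mean difference | Mann-Whitney: cheaper | t-test: cheaper |
|---|---|---|---|---|---|
| 400 | 0.1 | 15% vs 5% | 800 − 400 = +400 | 99.8% | 0.1% |
| 200 | 0.1 | 12% vs 6% | 480 − 200 = +280 | 77.5% | 0.1% |
| 200 | 0.3 | 12% vs 6% | +280 | 6.8% | 0.2% |
| 200 | 0.6 | 12% vs 6% | +280 | 2.3% | 0.2% |
| 50 | 0.3 | 12% vs 6% | 480 − 50 = +430 | 0.7% | 0.0% |

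Over all 32 combinations run (savings 20 to 400, log SD 0.05 to 0.6, two pairs of readmission rates), the false result ranged from 0% to 100% for Mann-Whitney and was at most 2.3% for the t-test.

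**Reading.** Reversal needs a routine saving that is large relative to the spread of ordinary costs. With a small saving and widely spread hospital costs it is rare. The antibiotic cost row was not simulated; for it the point rests on the mismatch between test and estimate.

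**The case against.** A reader might infer that the plan ignores mean cost, or that it would declare the short course cheaper when it is dearer. The text does not support that. The sentence in Section 9.4 that allows Mann-Whitney begins by committing to a mean difference with a 95% confidence interval, so a higher mean in the 6-day arm would be reported with its sign and uncertainty. Mann-Whitney supplies only a p-value, and the t-test is equally allowed. That skewness would lead to the rank test is an inference from common practice, not something the plan says.

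A reader might also take 82% as the expected error rate. It is not. That figure assumes a routine cost of about 60 euro and leaves out the index admission. The outcome is total treatment-associated cost, every patient was admitted (Section 4.2), and nothing in Section 7.3.4 limits costs to the period after randomisation. With an index admission of the assumed size, that scenario almost vanishes.

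Finally, costs are a secondary outcome, the economic analyses are named separately, and nothing says a rank test would drive them.

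All of this stands and limits the point. It does not remove it: the test is still not fixed in advance, one of the two permitted tests does not address the promised estimate, and no interval method for skewed costs is given.

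**Conclusion.** The point holds in a narrow form. For both cost rows, the plan allows a p-value that tests a different quantity from the mean difference it promises, and does not say when. The two can disagree, and in some cost structures they point in opposite directions.

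How often that would happen cannot be settled from the documents. Under assumed costs with a truly dearer 6-day arm, Mann-Whitney favoured that arm in anything from 0% to 100% of trials, depending mainly on the routine saving relative to the spread of ordinary costs and on whether the index admission is counted. A mean-based test stayed at or below about 2% throughout. The case for change rests on that contrast and on matching test to estimate, not on any single percentage.

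Neither the primary non-inferiority conclusion nor the sample size is affected. This is an inexpensive improvement worth making to a secondary analysis.

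**What to change.** In Section 9.4 and Table 3, for total treatment-associated costs and total antibiotic costs:

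- Name the difference in arithmetic mean cost per patient as the estimate.
- Prespecify its 95% confidence interval, by bootstrap or Welch.
- Take any p-value from the same comparison of means.
- Delete the Mann-Whitney option from these two rows.
- State whether total cost includes the index admission, since this governs the spread of the outcome.

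The cost is SAP wording and a few lines of code, with no new data or patients. The mean-based interval may be wide, and power for cost will be modest: in the scenario with saving 200, log SD 0.1 and a true difference of +280, the t-test found the 6-day arm significantly dearer in only 11.5% of trials. That is a fair picture of what 158 per arm can say about mean cost.
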